Given the difficulty in randomizing patients (high cost of phenoxybenzamine has caused a large portion of patients crossing over to the doxazosin arm, resulting in unbalance between the number of patients in each arm), patients who have been pre-treated with doxazosin before pheochromocytoma resection prospectively followed during the course of this study will be compared to a retrospective group of patients who were pre-treated with phenoxybenzamine.

Descriptive statistics including mean, median, standard difference, and frequencies will be calculated for each of the variables measured.

Differences in hemodynamic instability as indexed by specific vital sign parameters, ICU length of stay, inpatient length of stay, morbidity, mortality, cost, and quality of life will be analyzed with t tests or non-parametric tests as appropriate.

1.3 *If you will conduct genetic analysis with specimens, provide your assurance that the results will not be disclosed to subjects or used for clinical care.

Agree	
Not Applicable	

2.0 *Describe specimens and/or data that will be acquired without direct contact with study participants. Complete this item for each type used in the study:

usea in the stu	uy.	
Source	Data and/or Specimens Information	
View UCLA medical records	Data and/or Specimens? Indicate all that apply:	Data
	Indicate whether the data and/or specimens are pre-existing, at the time of this study, and/or if collection will be prospective:	Pre-existing
	Describe the data and/or specimens and indicate the original collection dates:	Electronic medical records from patients undergoing adrenalectomy for pheochromocytoma or paraganglioma from January 1, 2015 to present. Please see item 4.0 for further details on data to be collected from the EMR.
	Indicate the approximate number of data records and/or specimens to be collected:	50
	Will the specimens be used with animals?	No
	If yes, indicate the IACUC Number:	No Value Entered

*If any sources of data and/or specimens are not at UCLA, provide your agreement that the appropriate institutional approvals for release will be obtained (e.g., IRB approval).

Agree

•	
Not Applicable	
	o third parties, please contact the CTSI for directions about additional requirements. sources/pages/third_party
nttps://www.ctsi.ucla.edu/researcher-re	sources/pages/third_party
uttps://www.ctsi.ucla.edu/researcher-re	

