PATIENT ACQUISITION. All patients referred to the UCLA Department of Surgery requiring surgical resection of pheochromocytoma or paraganglioma will be counseled about surgery and the necessity for preoperative alpha blockade. The benefits and risks of the study will discussed, and the patient will be given the opportunity to enroll. Upon obtaining informed consent regarding enrollment in the study, the patient will be randomized to either receive preoperative blockade with either phenoxybenzamine or doxazosin.

PREOPERATIVE PREPARATION. The patient will then be referred to the UCLA Preoperative Evaluation and Planning Center (PEPC) for preoperative planning and optimization by an attending anesthesiologist. Additional testing such as echocardiography or stress testing will be pursed in accordance with preoperative risk-stratification in the standard fashion. A few weeks prior to surgery, the patient will initiate preoperative alpha blockade with the drug as determined by randomization. The drug will be titrated to a blood pressure of 120-130/80-85 in the standard fashion. Adjunctive beta blockers or calcium channel blockers may be initiated at the discretion of the physician.

Titration will be performed utilized the attached log ("Medication and Blood Pressure Log"), which will be emailed to the patient and will be returned by the patient by email every 2 days. The patients sitting and standing blood pressure will be used to titrate their alpha blocker dosage to prespecified targets as noted in the original IRB proposal. Heart rate will be logged to determine whether the patient requires adjunctive

specified targets as noted in the original IRB proposal. Heart rate will be logged to determine whether the patient requires adjunctive antihypertensive medications such as beta blockers or calcium channel blockers. This titration will take place over a period of 2-3 weeks. Once the patient's alpha blockade titration is complete, the log will be saved in a secure, encrypted server and will be linked with the patients record using non-identifying record ID.

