INTRAOPERATIVE PROTOCOL. Intraoperative hemodynamic monitoring will be conducted in the standard fashion, and a phenylephrine dose response curve will be generated by titration with phenylephrine to estimate the ED30 and therefore the effectiveness of the blockade. Surgery will proceed in the standard fashion. Times of induction, tumor manipulation, and adrenal vein ligation will be recorded. Vasopressors will be used at the discretion of the anesthesiologist.

POSTOPERATIVE PROTOCOL. Patients will be taken to the PACU for routine postoperative care. Admission to the surgical ICU will be performed at the discretion of the attending anesthesiologist and surgeon.

QUALITY OF LIFE / DRUG ADVERSE EFFECTS. Data regarding patient health related quality of life and drug adverse effects will be collected at five time points pre-blockade, post-blockade, and postoperatively at 3 months, 6 months, and 1 year. Health related quality of life data will be assessed utilizing the Short Form-36. Patients will be queried to specific adverse effects such as nasal congestion, headaches, palpitation, as well as their frequency and level of distress caused. Surveys will be complete in person during routine encounters or over the phone.

COST. Preoperative drug costs will be determined using the average wholesale price per unit multiplied by the number of units taken by the patient. Enrollment of the patient in Medicare and Medicare part D will be noted. Data regarding out of pocket drug costs will be collected. Inpatient costs will be calculated utilizing patient charges and the application of a charge to cost ratio.

4.1	* Will you be providing results of any experimental tests that
	are performed for the study?

o	Not Applicable
0	No
0	Yes - Complete Items 4.1.1 and 4.1.2

- 4.1.1 You indicated in Item 4.1 that the research involves experimental tests. Please describe the tests, provide a rationale for providing participants with the experimental test results and explain what, how and by whom participants and their health care provider will be told about the meaning, reliability, and applicability of the test results for health care decisions.
- 4.1.2 Will tests be performed by a Clinical Laboratory Improvement Amendments (CLIA) approved lab?

 Yes No

$^{5.0}$ *Indicate how much time will be required of the subjects, per visit or contact, and in total for the study.

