The time required of study subjects will includes time that will be standard for the care of the patient and unrelated to participation of the study. This involves preoperative evaluation by a surgeon (30 minutes) and anesthesiologist (30 minutes), inpatient surgery and routine inpatient postoperative care (average length of inpatient stay 2-3 days), and postoperative follow up (30 minutes).

Additional time required of the study subjects as related to the study would involve 5 questionnaires administered in person or by phone at the time points outlined above, with each administration of the survey taking approximately 5 minutes.

*Statistics and Data Analysis: Describe the proposed statistical procedures or descriptive analyses for the study. If applicable, indicate how the sample size was determined.

Descriptive statistics including mean, median, standard difference, and frequencies will be calculated for each of the variables measured.

This view has been locked by amendment(s)

Warning: Save your work at least every 15 minutes by clicking "Save" or "Continue."

Characteristics of the Study Population

1.0 *Is this an observational or ethnographic study for which the number of participants observed or interviewed cannot be determined in advance.

O Yes O No

- 2.0 If you answered "no" to item 1.0, indicate the maximum number of study participants you hope to enroll: 62
- 3.0 How many participants do you expect you will need to recruit, consent and/or screen to meet the target number above?
- *Indicate the specific inclusion criteria for enrollment of each of the groups of research participants in this study.

 If there are any inclusion criteria based on *gender, pregnancy/childbearing potential, race, ethnicity or language spoken*, explain the nature of and scientific rationale for the inclusions.

 Inclusion criteria include:

(1) Diagnosis of pheochromocytoma or paraganglioma as evidenced by appropriate biochemical evaluation and imaging.

- (2) Surgical resection recommended.
- (3) Patients aged 12 and older.
- *Indicate the specific exclusion criteria for each of the groups of research participants in this study.

 If there are any exclusion criteria based on gender, pregnancy/childbearing potential, race, ethnicity or language spoken, explain the nature of and scientific rationale for the exclusions.

 None.
- 6.0 *How (chart review, additional tests/exams for study purposes, etc.), when and by whom will eligibility be determined?

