- (1) Cost. The cost of prescription drugs in the United States is increasing, with the cost of some drugs increasing by over 1000% in the last decade.[1] Currently, the maximum listed wholesale price per unit of phenoxybenzamine is \$197.79 in contrast to \$1.42 for doxazosin[2]. In our anecdotal experience, an increasing number of patients are unable to afford phenoxybenzamine for preoperative alpha blockade prior to pheochromocytoma resection. As current studies show no differences in morbidity and mortality between selective and non-selective alpha blockade prior to pheochromocytoma resection, doxazosin is likely to represent a clinically equivalent option associated with significant cost savings.
- (2) Quality of life. Phenoxybenzamine is a long-acting, non-competitive, non-selective alpha blocker that crosses the blood brain barrier, causing centrally mediated side effects including headaches and sedation that limit the medication's tolerability. Patients who receive doxazosin in comparison to phenoxybenzamine prior to pheochromocytoma resection less frequently experience postural hypotension, nasal stuffiness, and headache.[3] In addition to being cost effective, doxazosin may also be associated with increased health related quality of life while receiving alpha blockade.

Overall, current retrospective data suggest that selective alpha blockade is as effective as non-selective blockade in addition to being less costly and associated with less frequent adverse effects. A randomized controlled trial demonstrating this will result in societal cost savings and increased health related quality of life in patients undergoing pheochromocytoma resection.

- [2] http://micromedex.com/Portals/1/Assets/AWP%20Policy_Oct%202014.pdf

Risks

*Indicate the potential risks/discomforts, if any, associated with each intervention or research procedure.

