		 Research participants will not be asked to sign a consent form or give oral consent 			
		Consent will be obtained by a collaborating institution.			
		1.1	- If you checked more than one plan above, list the study groups and the plan that you will use for each If you checked "Consent will be obtained by a collaborating institution", explain the consent process and upload a copy of the most recent approved consent document in item 1.2. Signed consent obtained from patients who were randomized to phenoxybenzamine or doxazosin. Requesting a waiver of consent for the retrospective cohort of patients who were pre-treated with phenoxybenzamine. If applicable, attach the consent document(s) from collaborating institution(s).		
			Document Name Document Version # There are no items to display		

View: NEW 20.3 - Description of the Consent Process

ID: IRB#17-000048

This view has been locked by amendment(s)

Warning: Save your work at least every 15 minutes by clicking "Save" or "Continue."

.0	*Indicate the	type of setting(s) in which the consent process will be conducted.
	Check all that	apply.
	☐ In a priva	
	In a priv	ate room
	☐ In a waiti	ng room
	n a publ	ic setting
	☐ In a grou	p setting
	On the ir	ternet
	✓ Over the	telephone
	Other	 
	1.1	If you checked more than one response, or indicated other, describe.
		If a patient meets inclusion criteria for the study, the study will be
		discussed with the patients at the time of surgical consultation in
		a private exam room by the attending surgeon and informed consent obtained at that time.
		If a patient has been already evaluated for surgery but has not yet received surgery and the study has not been introduced, a phone
		call will be made to the patient by an MD to discuss the study
		over the phone. The patient will be mailed a consent form to either return by mail or in person at their next visit.
		Cities return by mail of in person at their next visit.
		All patients enrolled in the study will have had an in person encounter with an attending surgeon prior to obtaining consent.
		encounter with an attending surgeon prior to obtaining consent.
	1.2	If the setting is not private, describe the measures to protect
.0		confidentiality or indicate "not applicable." measures that will be taken to provide prospective research participants with sufficient opportunity to consider whether or

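### The quality-of-life analysis names no key time point and no use of the pre-blockade SF-36 score, and its retrospective comparator has no named source of SF-36 data

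*Combined protocol and SAP*

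**What the plan says.** - **Instrument and schedule** (section 10.1, research design, quality-of-life paragraph): "Health related quality of life data will be assessed utilizing the Short Form-36". Data are to be "collected at five time points pre-blockade, post-blockade, and postoperatively at 3 months, 6 months, and 1 year", by surveys completed face to face or by telephone.
- **Test** (section 9.6, item 1.2): "quality of life will be analyzed with t tests or non-parametric tests as appropriate". No score, time point, covariate or repeated-measures method is attached to this.
- **Main statistics item** (section 10.1): "Descriptive statistics including mean, median, standard difference, and frequencies will be calculated for each of the variables measured". Nothing inferential follows in the readable text.
- **Where the benefit is expected** (Risks & Benefits, item 2.0, second heading): "doxazosin may also be associated with increased health related quality of life while receiving alpha blockade".
- **Time on drug** (section 10.1, preoperative preparation): "This titration will take place over a period of 2-3 weeks". Blockade is described throughout as preoperative.
- **Comparator** (section 9.6, items 1.2 and 2.0): a retrospective phenoxybenzamine group, from pre-existing UCLA medical records.
- **Consent** (section 20.1, item 1.1): "Signed consent obtained from patients who were randomized to phenoxybenzamine or doxazosin". A waiver is requested for the retrospective cohort.

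**The concern.** The plan collects the pair of measurements needed for its quality-of-life claim, one before the drug and one on it, but does not commit to using them as a pair. That leaves the time point and the form of the score (raw, change or adjusted) open until the data are seen. A raw post-blockade comparison would lose precision in a small sample. Because the groups are no longer cleanly randomised, it would also let a starting difference pass as a drug effect.

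The comparator is the larger obstacle. Quality of life is among the outcomes on which section 9.6 hypothesises that doxazosin is not inferior, yet the group named for comparison has no stated SF-36 scores.

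**Working it through.** **1. The plan's own figures.** None depends on this point. The target of 62 has no effect size, SD, power, final alpha or margin behind it, so it cannot be re-derived. The screening number does reproduce: 62 / 0.85 = 72.9, rounded up to 73. Everything in steps 4 to 7 is illustration under stated assumptions.

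**2. Which survey measures the on-drug period.**

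| Survey | Position |
|---|---|
| Pre-blockade | before drug start |
| Post-blockade | after drug start, before resection |
| 3 months, 6 months, 1 year | after resection |

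Only the second row bears directly on quality of life while taking the blocker, and the first row is its baseline.

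**3. Who can have scores.**

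| Group | SF-36 as described |
|---|---|
| Prospective doxazosin | study surveys |
| Consented, randomised to phenoxybenzamine | study surveys; number not stated |
| Retrospective phenoxybenzamine | existing records; no SF-36 source named |

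The records entry in section 9.6 points to an item 4.0 for details, apparently the research design item of section 10.1. That item describes SF-36 as a survey given to participants, not as a chart variable.

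**4. Gain from adjustment.** Let r be the correlation between pre- and post-blockade scores (assumed), with equal variances. Relative to a post-score test, the variance of the group difference is 1 − r² for ANCOVA and 2(1 − r) for a change score. Their ratio is (1 + r)/2.

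| r | ANCOVA, 1 − r² | Cut against post score | Change score, 2(1 − r) | Ratio, (1 + r)/2 | Cut against change score |
|---|---|---|---|---|---|
| 0.3 | 0.91 | 9% | 1.40 | 0.65 | 35% |
| 0.5 | 0.75 | 25% | 1.00 | 0.75 | 25% |
| 0.7 | 0.51 | 49% | 0.60 | 0.85 | 15% |

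These are large-sample factors. Estimating the slope, and any baseline imbalance, takes back a little of the gain.

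**5. What that means at this size.** Assume a true difference of 0.5 SD and two-sided 0.05. The 95% CI half-width in SD units is 1.96 × √(1/n₁ + 1/n₂) × √(1 − r²). Power is approximately Φ(0.5 / [√(1/n₁ + 1/n₂) × √(1 − r²)] − 1.96). Splits of 62 as 31/31 and 50/12 are assumed; the second shows a small phenoxybenzamine group.

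| | 31/31: half-width, power | 50/12: half-width, power |
|---|---|---|
| Unadjusted | 1.96 × 0.254 = 0.50, 50% | 1.96 × 0.321 = 0.63, 34% |
| ANCOVA, r = 0.3 | 0.47, 54% | 0.60, 37% |
| ANCOVA, r = 0.5 | 0.43, 62% | 0.55, 43% |
| ANCOVA, r = 0.7 | 0.36, 79% | 0.45, 59% |

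**6. Starting imbalance.** If the groups differ by an assumed 0.3 SD before treatment and there is no drug effect, an unadjusted post-blockade comparison is biased by r × 0.3: 0.09, 0.15 and 0.21 SD at r = 0.3, 0.5 and 0.7. With 31 per group the false-positive rate becomes 6.5%, 9.1% and 13.1%.

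**7. Separate tests.** If the four follow-up surveys were each tested at 0.05, the chance of at least one false positive would be 1 − 0.95⁴ = 18.5% under independence. Repeated scores on the same patients are positively correlated, so the true figure would be lower.

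**The case against.** A reader might infer that the plan throws the baseline away, or that it averages five surveys and so dilutes the on-drug comparison. The documents support neither. They are silent on how the pre-blockade score enters, and a t test on change from baseline would fit the wording. Nothing says that time points are pooled. If they were tested separately, the post-blockade comparison would not be diluted; the issue would be multiplicity.

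Other points on that side have force:

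- The statement tying the benefit to the on-drug period is tentative and sits among the societal benefits. The aims also cover postoperative outcomes, so the later surveys are not irrelevant, and the plan never gave them confirmatory status.
- The correlations are assumed, and at r = 0.3 the saving against a post-score test is small. The 0.05 threshold appears only in the interim stopping rule of section 15.2.
- Attachments listed in section 10.1, such as the study variables and timeline, are not available here and may say more.
- ANCOVA does not remove confounding from cost-driven crossover, and the phenoxybenzamine group with surveys may be very small.

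These points limit the size of the claim and the status of the result. They do not supply a key time point, a role for the baseline or a source of comparator scores.

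**Conclusion.** The point holds as a gap in specification and data source. In the readable text, quality of life has five surveys, simple two-group tests, no key time point, no stated use of the baseline, and a planned comparator without named SF-36 data. As described, the two-group comparison cannot be made with the retrospective group. That would change only if such scores exist and are identified.

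Baseline adjustment is worth having at any plausible correlation, with the sizes in step 4 resting on assumed values of r. It improves the analysis of patients who have surveys but cannot rescue the comparison with charts. Any between-drug estimate is exploratory: the phenoxybenzamine number is unstated and confounding remains. Quality of life is one outcome among several, so this should be corrected but does not undermine the rest of the plan.

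**What to change.** In sections 9.6 and 10.1, state that:

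1. The post-blockade SF-36 score is the main quality-of-life comparison, with the scale or summary score named in advance, since none is given now.
2. Among consented patients with surveys (doxazosin, and those randomised to phenoxybenzamine), the between-drug difference is estimated with a 95% CI by ANCOVA with the pre-blockade score as covariate. Say whether groups are as randomised or as treated, give the number in each, and label the result exploratory. No margin is stated, so it should not be read as a non-inferiority test.
3. The paired pre-to-post change in the doxazosin cohort is reported with a 95% CI as a description, not a drug comparison.
4. The 3-month, 6-month and 1-year scores are shown descriptively.
5. No SF-36 comparison is made with chart-only controls.

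**Cost:** analysis wording only. The baseline is already collected, and no visit or survey is added. The downsides are that postoperative scores become descriptive and the between-drug estimate may be imprecise.

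### The cost method names no price year, so if surgery years differ between the prospective doxazosin group and the retrospective phenoxybenzamine group, price change is counted as a drug effect

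*Combined protocol and SAP*

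**What the plan says.** The costing method is the COST paragraph of NEW 10.1, item 4.0. It has three parts:

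- **Drug cost:** "Preoperative drug costs will be determined using the average wholesale price per unit multiplied by the number of units taken by the patient".
- **Out-of-pocket cost:** "Data regarding out of pocket drug costs will be collected".
- **Inpatient cost:** "Inpatient costs will be calculated utilizing patient charges and the application of a charge to cost ratio".

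The paragraph shares item 4.0 with text that randomises each consenting patient to one of the two drugs. NEW 9.6, item 1.2, gives a different comparison: "patients who have been pre-treated with doxazosin before pheochromocytoma resection prospectively followed during the course of this study will be compared to a retrospective group" pre-treated with phenoxybenzamine. Item 2.0 of the same section describes the pre-existing data as records of "patients undergoing adrenalectomy for pheochromocytoma or paraganglioma from January 1, 2015 to present". Item 1.2 analyses cost, like the other outcomes, with t tests or a non-parametric alternative. It names no adjustment for year of surgery.

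Cost is listed among the outcomes and is part of the non-inferiority hypothesis in NEW 9.6, item 1.1. It is also one of the two societal benefits claimed in Risks & Benefits, item 2.0. That item remarks that drug prices move over time, "with the cost of some drugs increasing by over 1000% in the last decade".

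**The concern.** Under concurrent randomisation, a missing price year does little harm, because calendar time is balanced between the arms and price change falls on both alike. The comparison in NEW 9.6 removes that protection. Drug is now tied to the way patients entered the study, and possibly to the period in which they were treated.

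A charge-to-cost ratio does not solve this. Even a ratio specific to each year only turns that year's charges into that year's costs. It does not bring different years to one price level. If the two groups had surgery in different years, the cost contrast therefore contains a price-level component that has nothing to do with the drug, and the planned test cannot separate the two. At stake is whether a reported difference in hospital cost, or the lack of one, can be read as an effect of the choice of alpha blocker.

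**Working it through.** **Figures in the plan.** There is no cost difference, cost variance, inflation rate or price year to reproduce. The only cost figures are the unit prices in Risks & Benefits, item 2.0: $197.79 for phenoxybenzamine and $1.42 for doxazosin. Their difference is 197.79 − 1.42 = $196.37, and their ratio is 197.79 / 1.42 = about 139.

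**Step 1: what the inpatient formula leaves in.** For a patient discharged in year t, the stated cost is charges(t) × ratio. There are two readings:

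- If one fixed ratio serves all years, the whole growth in charges passes into cost.
- If the ratio is that of the discharge year, growth in charges beyond growth in costs drops out, but growth in costs remains.

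Neither reading puts the groups on one price level. The calculation below uses cost growth, the smaller component whenever charges outpace costs.

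**Step 2: size on assumed inputs.** Let r be annual cost growth and g the mean gap in surgery year, with phenoxybenzamine earlier. If true resource use is equal, the apparent excess in the doxazosin group is (1 + r)^g − 1. Neither r nor g is in the documents; the values below are assumptions.

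| Cost growth r | g = 0 | g = 2 years | g = 5 years |
|---|---|---|---|
| 3% | 0% | 1.03² − 1 = 6.1% | 1.03⁵ − 1 = 15.9% |
| 5% | 0% | 1.05² − 1 = 10.25% | 1.05⁵ − 1 = 27.6% |

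The record window opens on January 1, 2015 and the form carries a print date of 12/15/21, a span of almost 7 years. A 5-year mean gap is therefore near the top of what is possible. Zero is also possible, because the window has no closing date before the present.

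**Step 3: direction, by component.**

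- *Inpatient:* with earlier controls and rising prices, doxazosin looks dearer than it is.
- *Out-of-pocket:* these are amounts from each patient's own year, so the same mixing occurs, but the direction depends on each drug's price path.
- *Drug cost at wholesale price:* if one price per drug is used for everyone, there is no calendar effect. If each patient's own date is used, there is. The text does not say which. With a roughly 139-fold gap in unit price, ordinary drift is unlikely to reverse this contrast.

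**Step 4: after indexing.** With every cost on one price year, the price-level part of the difference is removed, to the extent that the index tracks local prices. No corrected cost can be given, because the documents contain no patient-level costs or dates.

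**The case against.** The strongest reply is that no gap has been shown. Records run to the present, neither group's surgery dates are given, and the bias vanishes if the years coincide. This stands, and it is why the point is conditional. It does not rescue the method, which has no safeguard if the years differ.

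A second reply is that the cost benefit the plan claims is drug cost, that one wholesale price per drug may already be intended, and that the inpatient bias would be conservative for a non-inferiority claim about doxazosin. Most of this stands too. But inpatient cost is part of the costing, a conservative bias is still a wrong estimate, and it could hide a real hospital saving.

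A third reply is that the Study variables attachment may settle the price basis. It is listed in NEW 10.1 but not among the text available, so this cannot be checked.

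A reader might infer more than the documents support in four ways:

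- **That the cost result is certainly biased.** This needs a gap in surgery year, which is not documented.
- **That a particular false-positive rate follows.** It would need a cost variance and group sizes. The 62 is the maximum total enrolment, and the section describing recruitment still randomises to both drugs. The 50 is an approximate number of records, not stated to be phenoxybenzamine patients only. The doxazosin group size is not stated.
- **That the remark on price rises of over 1000% applies here.** It concerns some drugs, not these two.
- **That units taken are counted differently in the two groups.** Prospective patients have a log that "will be returned by the patient by email every 2 days", but the plan describes it for titration, not costing. Replacing units taken with prescribed or dispensed units would change the quantity measured.

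**Conclusion.** The concern holds in conditional form. The stated cost method has no common price year, and the comparison in NEW 9.6 is no longer protected by concurrent randomisation. Wherever surgery years differ between the groups, price change enters the inpatient and out-of-pocket contrasts and is read as a drug effect.

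The inpatient comparison is the most exposed. On assumed cost growth of 3-5% a year, the spurious difference there is 0% with no gap, about 6-10% at 2 years and about 16-28% at 5 years, against doxazosin if the controls are earlier. The documents supply neither the growth rate nor the gap, so these figures show scale and do not estimate the bias. The wholesale drug-cost contrast is unlikely to change direction.

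**What to change.** Amend the COST paragraph before the cost analysis, in four steps:

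1. Convert inpatient charges with the charge-to-cost ratio of the discharge year.
2. Index all inpatient and out-of-pocket costs to one stated price year with a named, published medical-price index.
3. Value drug units in both groups from one dated wholesale price list.
4. Report the distribution of surgery year by group, so that readers can see how much indexing had to do.

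The cost is wording and a little extra analysis, using discharge dates and charges the costing already needs. Settling the price basis now also avoids choosing it after the results are seen. The limit should be stated alongside: indexing removes price-level change only. Changes in practice over time, such as ICU use or length of stay, would remain mixed with the choice of drug.
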